7.5 Follow-up Visit 11 (Day 36) (Allowable window: Days 33 - 43)

The following procedures and assessments will be performed at the Follow-Up Visit 11, Day 36:

- 1. Participants will return on Day 36 (Monday or Tuesday). With staff they will review symptoms, concomitant medications, and any medical problems since the last visit, which will be recorded on the appropriate CRF.
- 2. Focused medical, gynaecological and sexual history since the last visit to include assessment of STI risk.
- 3. Symptom-directed physical and pelvic examination by a study physician or nurse that will include vital signs, including temperature, as well as assessment of symptoms and adverse events.
- 4. The pelvic examination will be conducted in the following order:
  - a. Examination of the external genitalia
  - b. Speculum insertion and examination of vagina, fornices and cervix with naked eye. Water will be used to ease speculum insertion. No lubricant should be used as it could contain chlorhexidine which may kill *Lactobacillus.*
  - c. Vaginal pH
  - d. Vaginal swab for Gram stain (Nugent scoring system)

- e. Two Vaginal swabs for complete mucosal sampling including identification of vaginal bacteria, lactobacilli species, cytokines and HIV target cells as well as multiomic (e.g. proteomics, metabolomics, etc.) testing
- f. Vaginal swab for prostate specific antigen testing as a proxy for recent exposure to semen
- g. Vaginal swab for STI testing if indicated by symptoms
- h. A cervicovaginal lavage sample
- i. Vaginal swabs for *L. crispatus* identification with qPCR If indicated, cervical (or vaginal) swabs for nucleic acid amplification of *N. gonorrhoeae, and C. trachomatis.*
- 5. Dipstick on clean catch urine; if abnormal, urinalysis (UA) will be performed.
- 6. Rapid Urine βhCG pregnancy test
- 7. All clinical and laboratory findings at the time of the evaluation will be recorded on the CRF. These findings will include observations present on the pelvic exam such as genital findings including location; presence or absence, and character of vaginal or cervical discharge or lesions; and results of any on site tests.
- 8. Participants will be reminded not to use tampons or any other vaginal products throughout the study.
- 9. Participants will be counselled to try to abstain from sexual intercourse for 12 hours before the Final Visit 19 (Day 64).
- 10. Participants will receive non-spermicidal lubricated condoms for their male sexual partners. Participants will be encouraged to use condoms if they engage invaginal intercourse throughout the study.
- 11. Participants will be asked to complete a detailed self-administered questionnaire assessing the acceptability of the study product and the applicator.

Women with vaginal discharge or vaginitis symptoms during the Follow-Up Visit 11 will be referred for standard treatment. If the test results at the follow-up visit suggest a urinary tract infection, cervicitis or vulvovaginitis, the participant will be referred for standard treatment.

If the clinician suspects the woman to have developed an STI since the last visit, appropriate tests will be conducted and if needed the woman will be referred to standard of care treatment in compliance with current CDC Treatment Guidelines.

Women who develop *symptomatic* BV confirmed by Nugent 7-10 on Gram stain at least 4 weeks after the last Metronidazole treatment will be retreated with Metronidazole. This practice follows CDC treatment guidelines and FDA recommendations. The 7-day course of Metronidazole will begin as soon as possible. Women diagnosed with *asymptomatic* BV during the follow-up visit will not be retreated with Metronidazole.

If test results and clinical screening suggest a UTI, the woman will be managed as clinically indicated.

Participants who test HIV-positive after randomization, will discontinue study product, but continue follow-up and attend all remaining study visits to monitor for adverse events.

HIV-specific care, including the provision of antiretroviral treatment and ongoing management will be provided by the FRESH Study.

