#### 2.6 Potential Risks and Benefits

#### 2.6.1 Potential Risks

#### 2.6.1.1 Biological Risks: LACTIN-V and Placebo

The study product contains a naturally occurring strain of *L. crispatus* CTV-05. To date, there has been considerable amount of experience using LACTIN-V at concentrations up to  $2 \times 10^9$  cfu/dose without any apparent related adverse effects, with the exception of a short duration of asymptomatic vaginal discharge. No serious adverse events have been reported in Protocol No. LV-001, LV-002 and LV-004 using LACTIN-V at 5 x 10^6 and 5 x 10^8 cfu/dose, and no subject left the protocol due to an adverse event. No severe or severe-related adverse event has been experienced by more than one subject. In Protocol No. LV-003, using LACTIN-V at 5 x 10^8 cfu/dose, one subject in the placebo group experienced three simultaneous SAEs unrelated to LACTIN-V. Two subjects in the LACTIN-V group discontinued study treatment due to AEs; one subject became pregnant and the other reported nausea and diarrhea, which required treatment.

Safety results of the recently completed Phase 2a trial (LV-006) assessed colonization efficiency, safety, tolerability and acceptability of LACTIN-V at 2 x 10^9 cfu/ dose in 24 women with BV. No Grade 3 AEs or SAEs were observed during the clinical phase of the study. Based on the DAIDS Toxicity Table Addendum for Vaginal Microbicide Studies (November 2007)  designed to standardize AE assessment, a total of 120 total AEs were reported, 108 (90%) of which were Grade 1 and 12 (10.0%) were Grade 2 severity. The most common genitourinary AEs included vaginal discharge of study product (46%), abdominal pain (46%) and dysuria (21%). AEs were evenly distributed between LACTIN-V and placebo groups. All enrolled women (n=24) reported at least one AE. A single participant receiving placebo discontinued herself from study product due to a moderate AE (vaginal irritation).

Risks from the administration of LACTIN-V are low since colonization with this type of organism is strongly associated with improved vaginal health. No systemic risks are anticipated since this is an organism that is applied topically and not expected to be absorbed. These risks will be explained in the written informed consent form. No pregnant women, fetuses, prisoners, children, persons with an active STI or women undergoing in vitro fertilization are included in this study.

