**Brief Check-in Follow-up Visits 4 - 10 (Days 11, 15, 18, 22, 25, 29 and 32)** without physical and gynaecological exams to assess adherence, menstrual cycle, sexual activity, condom use, concomitant medications, and AEs, and to administer subsequent doses of study product are scheduled to coincide with regular clinic visits as part of the FRESH schedule (twice weekly either Monday/Thursday or Tuesday/Friday).

Week 1:	Day 8 (where the doses for Day 9 & 10 are handed to participants to take at
	home)
	Day 11 (where the dose for Day 12 is handed to participants to take at home)
Week 2:	Day 15 and 18 (Doses 6 and 7) administered in clinic
Week 3:	Day 22 and 25. (Doses 8 and 9) administered in clinic
Week 4:	Day 29 and 32. (Doses 10 and 11) administered in clinic

At the beginning of Week 5, at the end of the dosing phase, a **Follow-up Visit 11** is scheduled for **Day 36**. This visit will include a physical and gynaecological exam to collect vaginal microbiome data, including cervical swabs, cervicovaginal lavage fluid and an endocervical cytobrush to assess the microbial composition, cytokines and mucosal HIV target cells. A gram stain and a vaginal swab for L. crispatus (including CTV-05) identification will be collected.

Should symptoms or the sexual history suggest the acquisition of an STI, testing for STIs will be included. Acceptability will be assessed using a questionnaire.

During Week 5 – 8, study staff will continue to check in with participants twice weekly for brief **Checkin Follow-up Visits 12 – 18 (Days 39, 43, 46, 50, 53, 57 and 60)** without physical and gynaecological exams to assess menstrual cycle, sexual activity, condom use, concomitant medications, and AEs. These are scheduled to coincide with regular clinic visits as part of the FRESH schedule (twice weekly either Monday/Thursday or Tuesday/Friday).

Week 5:	Day 39
Week 6:	Day 43 and 46
Week 7:	Day 50 and 53
Week 8:	Day 57 and 60

The **Final Visit 19 (Day 64)** 4 weeks post dosing will include a physical and gynaecological exam to collect vaginal microbiome data, including cervical swabs, cervicovaginal lavage fluid and an endocervical cytobrush to assess the microbial composition, cytokines and mucosal HIV target cells. A gram stain and a vaginal swab for L. crispatus (including CTV-05) identification will be collected. Should symptoms or the sexual history suggest the acquisition of an STI, testing for STIs will be included.

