Coinciding with the regular twice weekly visits of the FRESH study, brief Check-in Visits will be conducted, during which directly observed product administration of the remaining doses will occur (Doses 4 - 11).

- a. Check-In Visit 4 (Day 11), Dose 4 (Dose 5 to take home for Day 12)
- b. Check-In Visit 5 (Day 15), Dose 6
- c. Check-In Visit 6 (Day 18), Dose 7
- d. Check-In Visit 7 (Day 22), Dose 8
- e. Check-In Visit 8 (Day 25), Dose 9
- f. Check-In Visit 9 (Day 29), Dose 10
- g. Check-In Visit 10 (Day 32), Dose 11

The following short assessments will be performed at these Check-In Visits 4 - 10:

- 1. Staff will review symptoms, concomitant medications, last menses, sexual activity and any medical problems since the last visit, which will be recorded on the appropriate CRF.
- 2. The participant will be asked to provide exact dates and times of those study product administrations that took place at home (Dose 2,3 and 5 only).
- 3. Staff will hand the appropriate dose (4, 6- 11) to the participant from the carton stored on site, labeled with the participant's study ID.
- 4. In Week 1 only, staff will hand the fifth dose to the participant from the carton on site, to take home and self-administer the next day (Day 12)
- 5. Staff will document the study product administration on the appropriate CRF.
- 6. Participants will be reminded not to use tampons or any other vaginal products throughout the study.
- 7. Participants will be encouraged to use the provided non-spermicidal condoms if they engage in vaginal intercourse throughout the study.
- 8. Participants will be counselled to try to abstain from sexual intercourse for 12 hours after each study product application and for 12 hours before those study visits that include a gynaecological exam.
- 9. An appointment for the next Check-In, Follow-Up or Final Visit will be confirmed or rescheduled if necessary. Depending on the time of the enrolment and the average length of the participant's menstrual cycle, careful attention should be paid to the approximate time of the participant's next menstrual period when scheduling those visits. Later adjustments of those dates may be necessary.

If the participant fails to cancel the appointment and reschedule, and she is unreachable during the agreed upon time for the telephone interview, the study team will make three attempts to reach the participant to reschedule the telephone interview.

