## 8.2 Laboratory Evaluations

8.2.1 Clinical Laboratory Evaluations

At the clinical site, the following tests will be performed using approved standard inhouse tests:

- Pregnancy will be tested by standard rapid urine βhCG assays.
- Urine will be tested by urine dipstick for evidence of urinary tract infection, with follow-up urinalysis (UA), if abnormal.
- HIV testing will be conducted using standardized algorithms.\*
- Cervical (or vaginal) swabs will be tested for *N. gonorrhoeae*, *T. vaginalis*, *Mycoplasma genitalium* and *C. trachomatis* by nucleic acid amplification.
- Gram-stained vaginal smear by Nugent's scoring system for diagnosis of BV
- 8.2.2 Special Assays or Procedures
  - Vaginal specimens will be analyzed for vaginal colonization with *L. crispatus* using qPCR assays and 16S rRNA gene/shotgun sequencing, which will be performed by a central laboratory at the Ragon Institute of MGH, MIT and Harvard
  - Cervicovaginal lavage (CVL) specimens will be analyzed for cytokines and chemokines using a luminex array
  - Cervical cytobrush samples will be used to assess presence of HIV target cells by flow cytometry.
  - Vaginal specimens will be analyzed using multiomic (e.g. proteomics, metabolomics, etc.) testing.
  - Vaginal samples will be used for culturing of live bacterial isolates for quenching and functional analysis
  - CVL will also be used for in vitro anti-HIV activity assays

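### The Visit 11 window is set in study days and opens 1 day after the last scheduled dose, so residual product could raise Day 36 Lactobacillus positivity in the LACTIN-V arm only

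*Combined protocol and SAP*

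**What the plan says.** Section 7.5 carries the heading "7.5 Follow-up Visit 11 (Day 36) (Allowable window: Days 33 - 43", and Appendix A repeats the same range. The nominal visit is stated as "Participants will return on Day 36 (Monday or Tuesday", to match the FRESH clinic days. For Week 4 of the dosing phase, Section 4.0 lists "Day 29 and 32. (Doses 10 and 11) administered in clinic"; Sections 7.3 and 7.4 both list "g. Check-In Visit 10 (Day 32), Dose 11".

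The dosing visits (4 to 10) have no stated window. Section 7.4 says of appointments: "An appointment for the next Check-In, Follow-Up or Final Visit will be confirmed or rescheduled if necessary". Where menses affect scheduling, Sections 7.3 and 7.4 add: "Later adjustments of those dates may be necessary". No section sets a minimum number of days between the last dose and the Visit 11 samples.

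Visit 11 feeds two Objective 2 outcomes in Section 3.4.1. One is a Lactobacillus-dominant cervicotype after four weeks of treatment, labelled primary there. The other is successful colonization with CTV-05. Both are read again at Day 64. Section 8.2.2 says that colonization is assessed "using qPCR assays and 16S rRNA gene/shotgun sequencing". Section 6.1 describes the placebo as lacking the CTV-05 strain. Section 11.5 compares strains and cervicotypes between arms with Fisher's exact test and has no analysis by time since last dose.

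**The concern.** Each LACTIN-V dose delivers 2 x 10^9 cfu of the organism that the assays look for. Sequencing and qPCR measure DNA, so on their own they do not separate resident bacteria from powder applied a day or two earlier. Section 8.2.2 also lists culture, but for functional work and not to define colonization. The plan gives no colonization threshold and no rule for residual product.

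The error can go one way only. A woman on placebo cannot carry over CTV-05 from her applicator; a woman on LACTIN-V can. Randomization and blinding do not remove this, because the cause is the product itself.

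Two results are exposed. The Day 36 difference between arms could be too large. The Day 36 level is also the starting point for judging persistence after dosing stops, so inflating it would make the fall to Day 64 look steeper and count against LACTIN-V. The window also mixes very different intervals under one end-of-dosing label.

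**Working it through.** **1. Dose-to-sample interval.** Inputs: last scheduled dose Day 32 (Sections 4.0, 7.3, 7.4); Visit 11 window Days 33 to 43, nominal Day 36 (Section 7.5, Appendix A); Visit 19 window Days 57 to 71, nominal Day 64 (Section 7.7). Interval = sampling day minus 32.

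| Visit | Window opens | Nominal | Window closes |
|---|---|---|---|
| 11 | 33 − 32 = 1 day | 36 − 32 = 4 days | 43 − 32 = 11 days |
| 19 | 57 − 32 = 25 days | 64 − 32 = 32 days | 71 − 32 = 39 days |

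**2. Two routes to a short interval.** With Dose 11 on schedule, sampling on Day 33, 34 or 35 gives 1, 2 or 3 days. With Visit 11 on Day 36, a Visit 10 rescheduled to Day 33, 34 or 35 gives 3, 2 or 1 days.

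**3. Why Visit 11 might be moved early.** Section 7.1 allows enrolment 12 days before expected menses, and Section 5.2 excludes only cycles shorter than 21 days. A woman enrolled on Day 1 with menses on Day 13 and a 23-day cycle would next bleed on 13 + 23 = Day 36. Staff are told to schedule around menses. Going earlier is one permitted response; going later, up to Day 43, is another.

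**4. The plan's own figure.** Section 11.3 states more than 88% power for 10% vs 50% with 20 placebo and 40 LACTIN-V women, using a two-sided Fisher's exact test at 5%. Exact enumeration of the two binomials gives 0.891, so the figure reproduces. It belongs to the cytokine endpoint and is not changed by this point. No power is stated for the Lactobacillus outcomes.

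**5. Sensitivity of the Day 36 comparison (assumed inputs).** Let true positivity be b in both arms, so that there is no real effect. Let r be the share of truly negative LACTIN-V women who read positive from residual product. Observed LACTIN-V positivity is b + (1 − b)r; placebo stays at b. For b = 10% and r = 10%, this is 0.10 + 0.90 × 0.10 = 0.19. The same enumeration gives the chance of a significant result favouring LACTIN-V:

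| True positivity b | r = 0 | 5% | 10% | 20% | 30% |
|---|---|---|---|---|---|
| 10% | 0.5% | 3.3% | 9.5% | 31% | 58% |
| 20% | 1.7% | 3.7% | 6.9% | 19% | 39% |
| 30% | 1.6% | 3.1% | 5.4% | 13% | 27% |

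The scale is small in women. At b = 10%, 36 of 40 LACTIN-V women are truly negative, so r = 5% is 1.8 women and r = 10% is 3.6. Neither b nor r comes from the documents. If carry-over is detectable only at 1 to 3 days, r cannot exceed the share of truly negative women who are sampled that early.

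**The case against.** The case for leaving the window alone has real force, and most of it limits the size.

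- **Early visits should be uncommon.** Days 33 to 35 fall on Friday to Sunday for the Monday/Thursday group and Saturday to Monday for the Tuesday/Friday group, off each group's own FRESH days. This stands. The window still permits them.
- **Clearance is unknown.** The documents do not say how long product stays detectable. The LV-006 adverse-event figure for discharge of study product (46%, Section 2.6.1.1) gives no timing, and it shows product leaving the vagina, not persisting as DNA. This stands.
- **The cervicotype outcome needs dominance, not detection.** Residual DNA would have to outweigh the rest of the community. This stands for the cervicotype. It protects the CTV-05 outcome less, since no threshold is defined there.
- **Day 64 is read separately**, 25 to 39 days after Dose 11, and the powered endpoint is cytokines. Section 4.0 even calls Objective 2 secondary. This stands, but it does not repair the Day 36 reading.
- **Dosing is documented on the CRF**, so time since last dose can be derived without touching the window. This is true, and the fix uses it, but the plan does not commit to doing so.

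A reader might also infer that a missed dose would be made up at the next FRESH visit, putting Dose 11 on Day 36 itself. The documents do not support that. No section provides for make-up doses, Section 7.3 places Visit 11 after dosing is complete, and Appendix A shows no product dispensing at Visit 11. If Dose 11 is simply missed, the last dose is on Day 29 and the gap to Day 36 lengthens to 7 days.

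**Conclusion.** The defect is confirmed, and its size is unknown. The window permits sampling 1 to 11 days after the last scheduled dose, nothing ties it to the last actual dose, and any carry-over favours one arm at Day 36. That much follows from the schedule, the assay description and the placebo composition.

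A reader might go further and expect a tenth to a third of LACTIN-V women to read falsely positive, or treat the Day 36 result as unreliable. The documents do not support either. The shares in the table are assumptions, early visits are probably few, and at r = 5% the chance of a false finding is 3.1% to 3.7%, not far above the nominal 2.5% in one direction. The table shows only that the comparison becomes fragile if carry-over reaches 10% to 20% of truly negative women.

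The Day 64 Lactobacillus reading and the cytokine power figure are largely unaffected, although persistence measured from Day 36 inherits any inflation at its starting point. This is a worthwhile, inexpensive improvement to a Day 36 Objective 2 outcome and not a threat to the trial as a whole.

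**What to change.** In Section 7.5 and Appendix A, define the Visit 11 sampling window from the last dose actually taken. Use the plan's own nominal gap of 4 days as the lower limit and keep Day 43 as the upper limit. For a woman dosed on schedule this gives Days 36 to 43, that is 4 to 11 days after the dose. Day 33 can remain as a calendar floor, so that women who stopped product early are not sampled sooner than now. The change concerns sampling only and leaves the dosing schedule as it is.

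In Section 11.5, derive days since last dose from the dosing records on the CRF and report them by arm. Add a sensitivity analysis of the Day 36 Lactobacillus and CTV-05 outcomes restricted to samples taken at or beyond the 4-day gap.

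Cost: no new data and no change in sample size. Up to three early days for scheduling around menses are lost, at a visit that also supplies the cytokine endpoint; later days through Day 43 remain. The 4-day minimum restates the plan's nominal interval and is not backed by clearance data, so it narrows the problem without proving it absent.

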7.6 Check-In Visits 12 –18

Coinciding with the regular twice weekly visits of the FRESH study, brief Check-Visits will be conducted.

- a. Check-In Visit 12 (Day 39)
- b. Check-In Visit 13 (Day 43)
- c. Check-In Visit 14 (Day 46)
- d. Check-In Visit 15 (Day 50)
- e. Check-In Visit 16 (Day 53)
- f. Check-In Visit 17 (Day 57)
- g. Check-In Visit 18 (Day 60)

The following short assessments will be performed at these Check-In Visits 12 – 18:

- 1. Staff will review symptoms, concomitant medications, last menses, sexual activity and any medical problems since the last visit, which will be recorded on the appropriate CRF.
- 2. Participants will be reminded not to use tampons or any other vaginal products throughout the study.
- 3. Participants will be encouraged to use the provided non-spermicidal condoms if they engage in vaginal intercourse throughout the study.
- 4. Participants will be counselled to try to abstain from sexual intercourse for 12 hours after each study product application and for 12 hours before those study visits that include a gynaecological exam.
- 5. An appointment for the next Check-In will be confirmed or rescheduled if necessary.
- 6. At Check-In Visit 18: The appointment for the Final Visit 19 (Monday or Tuesday) will be confirmed. Depending on the time of the enrolment and the average length of the participant's menstrual cycle, careful attention should be paid to the approximate time of the participant's next menstrual period when scheduling those visits. Later adjustments of those dates may be necessary.

If the participant fails to cancel the appointment and reschedule, and she is unreachable during the agreed upon time for the telephone interview, the study team will make three attempts to reach the participant to reschedule the telephone interview.

7.7 Final Study Visit 19, Day 64 (Allowable window: Days 57 - 71)

The following procedures and assessments will be performed at the Final Visit 19, Day 64:

1. Participants will return on Day 64 (Monday or Tuesday). Staff will review symptoms, concomitant medications and any medical problems since the last visit, which will be

recorded on the appropriate CRF.

- 2. Medical, gynaecological and sexual history to include assessment of STI risk.
- 3. Symptom-directed physical and pelvic examination by a study physician or nurse that will include vital signs, including temperature, and examination of respiratory and cardiovascular systems, as well as assessment of symptoms and adverse events.
- 4. The pelvic examination will be conducted in the following order:
  - a. Examination of the external genitalia
  - *b.* Speculum insertion and examination of vagina, fornices and cervix with naked eye. Water will be used to ease speculum insertion. No lubricant should be used as it could contain chlorhexidine which may kill *Lactobacillus.*
  - c. Vaginal pH
  - d. Vaginal swab for Gram stain (Nugent scoring system)
  - e. Two Vaginal swabs for complete mucosal sampling including identification of vaginal bacteria, lactobacilli species, cytokines and HIV target cells as well as multiomic (e.g. proteomics, metabolomics, etc.) testing
  - f. Vaginal swab for prostate specific antigen testing as a proxy for recent exposure to semen
  - g. Vaginal swab for STI testing if indicated by symptoms
  - h. A cervicovaginal lavage sample
  - i. Vaginal swabs for *L. crispatus* identification with qPCR
  - j. Vaginal swab for prostate specific antigen testing as a proxy for recent exposure to semen
- 5. Dipstick on clean catch urine; if abnormal, urinalysis (UA) will be performed.
- 6. Rapid Urine βhCG pregnancy test
- 7. All clinical and laboratory findings at the time of the evaluation will be recorded on the CRF. These findings will include observations present on the pelvic exam such as genital findings including location; presence or absence, and character of vaginal or cervical discharge or lesions; and results of any on site tests.

Women with vaginal discharge or vaginitis symptoms at the Final Visit 19 will be referred for standard treatment.

If the test results and clinical screening at the follow-up visit suggest a urinary tract infection, cervicitis or vulvovaginitis, the participant will be referred for standard treatment.

If the clinician suspects the woman to have developed an STI since the last visit, appropriate tests will be conducted and if needed the woman will be referred to standard of care treatment in compliance with current CDC STI Treatment Guidelines.  The participant should be treated in case of positive findings.

Women who develop *symptomatic* BV confirmed by Nugent Score 7- 10 on Gram stain at least 4 weeks after the last Metronidazole treatment will be retreated with Metronidazole. This practice follows CDC treatment guidelines and FDA recommendations. The 7-day course of Metronidazole will begin as soon as possible. Women diagnosed with

asymptomatic BV during the follow-up visit will not be retreated with Metronidazole.

If test results and clinical screening suggest a UTI, the woman will be managed as clinically indicated.

Participants who test HIV-positive after randomization, will discontinue study product, but continue follow-up and attend all remaining study visits to monitor for adverse events. HIV-specific care, including the provision of antiretroviral treatment and ongoing management will be provided by the FRESH Study.

